18.1.9 Pain assessed using a VAS and FPS-R scale

For the calculation of daily average pain values of the Treatment Period per subjects, the following rules will be used:

- If the first IMP of the Treatment Period is administered in the morning, the daily average of “day 1” consists of the pain assessment in the evening of the same day and the morning pain assessment of the following day. All following daily averages will consist of an evening value and subsequent morning value.
- If the first IMP of the Treatment Period is administered in the evening, the daily average of “day 1” consists of the pain assessments in the morning and the evening of the following day. All following daily averages will consist of an morning and evening value on the same day.

18.1.10 Rescue medication

Correlation coefficients

The summary table for the number of daily doses and total daily dose per day of the Treatment Period include the mean amount of IMP (morphine equivalents; 1 mg morphine PR is equivalent to 2.5 mg tapentadol PR).

Additionally this table will provide for each day j , for each of the two endpoints k and each treatment arm l , Pearson’s and Spearman’s correlation coefficients of the tuples $(d_{i,j,l}, r_{i,j,k,l})$, where $d_{i,j,l}$ is the morphine equivalent amount of IMP of subject i on day j in treatment arm l , and $r_{i,j,k,l}$ is the number of daily doses ($k=1$) or mean total daily dose ($k=2$) of subject i on day j in treatment arm l . The correlation coefficients will be calculated using PROC CORR.

Time to first rescue medication intake

Time to first rescue medication intake will be calculated in hours as:

$$\text{date/time of first rescue medication intake} - \text{date/time of first IMP intake}$$

The information of date/time of first rescue medication intake will be taken from the eDiary. If the time of the first IMP intake is missing, 0:00 will be used if the first IMP intake was in the morning and 12:00 will be used if the first IMP was taken in the evening.

Censoring algorithm is defined as follows:

- Time to first rescue medication intake will be censored at the End-of-Treatment Visit (VE) regardless of whether subjects complete part 1 or perform Visit VE prior to day 14. The time to be considered for the censoring will be set to 23:59, or the time of first IMP intake of the Tapentadol Period if available.

[figure not shown]

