11.1.1.2 Visit V2 (Allocation Visit; Day 1)

If Visit V1 and Visit V2 are on the same day, the following procedures will not be repeated:

- Record age.
- Record concomitant medication intake/therapies.
- Perform a physical examination, document that it was performed, and record changes to previous assessment.
- Record body weight.
- Record vital signs (respiratory rate, systolic and diastolic blood pressure, and pulse rate).
- Assess and record adverse events.

The following Day 1 specific evaluations will be carried out:

- Perform a urine pregnancy test in female subjects who are post-menarchal or older than 12 years at the time of the scheduled visit.
- Check inclusion and exclusion criteria. Compliance with the exclusion criteria will be checked based on local laboratory values. The parameters needed for this assessment comprise: total serum bilirubin, serum albumin, aspartate transaminase, alanine transaminase, and serum creatinine. The creatinine clearance will be calculated automatically by the electronic CRF.

Confidential

Protocol KF5503-66
including Amendment 05Page 61 of 137
DMS version 9.0
27 Jul 2017

- Set up diary.
- Dispense diary.
- Instruct subject, parent(s), or legal guardian(s) on how to use diary.
 - Give instructions to record pain assessment twice daily in the diary (VAS and FPS-R) until Visit VE.
 - Give instructions to record intake of IMP and rescue medication in the diary, including time of administration.
- Record “pain right now” in the diary (VAS and FPS-R) before any painful or unpleasant procedure, and before the first intake of IMP as a baseline value.
- Complete the modified CAS.
- Allocate subject to treatment (see Section 10.3).
- Dispense IMP and rescue medication (see Section 10.6).
- Administer the first dose of IMP to the subject (see Section 10.2.1). The first dose of IMP will be taken during this visit, within 24 hours after randomization. Day 1 is the day of first IMP intake. Record administration in the diary.
- Train/instruct subject, parent(s), guardian(s), or caregiver on IMP/rescue medication use (handling and intake).
- Discuss IMP titration/dose adjustment.
- Take a single blood sample for serum pharmacokinetics from subjects on tapentadol PR at 1 hour to 6 hours after IMP for out-patients or at 3 hours to 6 hours after IMP intake for hospitalized subjects.

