7.2 SAP amendment rationale

7.2.1 Amendment 02

Amendment 02 to the final SAP was prepared to add a few additional analyses and refine some definitions and programming specifications:

1. Additional analyses:

- Analysis for the time to discontinuation from treatment due to “no more need for opioid treatment” during the Tapentadol Period was added, as this is one of the main reasons for discontinuation of treatment of Part 2.
- Summary statistics for the underlying diagnosis/reason for the pain leading to enrollment of the subjects in the trial.
- For all subjects, irrespective of age, one analysis of the primary endpoint based on VAS and one analysis based on FPS-R.
- Subgroup analyses of the primary endpoint for subjects with and without a neuropathic pain component to assess the effect of treatment depending on the type of the underlying pain.
- Overview of the individual response criteria to get a complete picture of reasons for subjects being responder or non-responder.

2. Programming specifications:

- Additional specifications to handle missing data were added:
 - If the time of the first IMP intake is missing, it will be imputed (by 0:00 in case of morning intake or 12:00 in case of evening intake) to derive the time from first IMP intake to first rescue medication intake.
 - In case of a missing intermediate visit during the Tapentadol Period, the visit date will be imputed to derive the average daily dose for the time frame between two scheduled consecutive visits.
 - In case of missing baseline pain intensity for the Tapentadol Period in the eCRF, the last available pain intensity value from the Treatment Period provided in the eDiary will be used as baseline.
 - Missing baseline pain intensities for the Treatment Period will be imputed using the multiple imputation that is used to impute the missing pain intensity values during the last 3 days of treatment.
- Consideration of deviations from the protocol with respect to the time point of visits in relation to IMP intakes:

- Protocol Amendment 02 specifies that subjects should receive their first IMP intake within 24 hours after randomization and that Day 1 is defined as the day of first IMP intake. Therefore, the definition of Day 1 of the trial in the SAP was updated accordingly to ensure clarity and consistency in the specification of Day 1. For the definition of the treatment completers, this redefined Day 1 of the trial will be considered.

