13.3.2 Rescue medication

The analyses of rescue medication address only Part 1. Rescue medication is assessed in the eDiary and assessed in the drug accountability page of the eCRF.

Analyses based on eDiary-data:

For each day of the Treatment Period (day 1 until day 16) the two endpoints

- Number of daily doses.
- Total daily dose (mg/kg).

will be summarized descriptively and compared to the mean amount of IMP (morphine equivalent) within the treatment arms of that day. The individual daily amount of IMP will be compared over time to the two endpoints with Pearson's and Spearman's correlation coefficients (see [Section 18.1.9](#) for details).

In addition, descriptive statistics will be presented for the subgroups as specified in [Table 4](#).

The time from first IMP to first rescue medication intake will be summarized using time-to-event methods. The calculation of time to first rescue medication and the censoring algorithm are described in [Section 18.1.9](#).

The percentage of days with rescue medication intake will be summarized descriptively as a categorical variable using the following percentage categories: 0, (0-10), [10-20), [20-30), ..., [90-100), 100. The percentages will be calculated considering the day of the first IMP intake up to the day of the last IMP intake of Part 1 (both included).

Analyses based on eCRF-data:

Based on information in the drug accountability page of the eCRF, the average mean daily dose for each subject, i.e., the cumulative volume difference between Visit V2 and Visit VE divided by the number of days between Visit V2 and Visit VE (both days included), will be analyzed descriptively.

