18.1.2.11 First and last IMP intake

The first and last IMP intake of the Treatment Period and of the Tapentadol Period will be specified based on the start and end dates provided on the IMP dispense form of the eCRF, supported by the eDiary data.

First IMP intake of the Treatment Period

The first IMP intake of the Treatment Period will be the date and time of the day (morning/evening) of the earliest start entry in the eCRF for the Treatment Period.

The time will be set to the time of the corresponding eDiary entry at that date and time of the day if available; else the time will be missing.

First IMP intake of the Tapentadol Period

The first IMP intake of the Tapentadol Period will be the date and time of the day of the earliest start entry in the eCRF for the Tapentadol Period.

The time will be set to the time of the corresponding eDiary entry at that date and time of the day if available; else the time will be missing.

Last IMP intake of the Treatment Period

The last IMP intake of the Treatment Period will be the date and time of the day of the latest end entry in the eCRF for the Treatment Period.

The time will be set to the time of the corresponding eDiary entry at that date and time of the day if available; else the time will be missing.

Last IMP intake of the Tapentadol Period

The last IMP intake of the Tapentadol Period will be the date and time of the day of the latest end entry in the eCRF for the Tapentadol Period.

The time will be set to the time of the corresponding eDiary entry at that date and time of the day if available; else the time will be missing.

In case the required information from the IMP Dispense form of the eCRF is not available, the first and last IMP intake assigned to the Treatment and Tapentadol Period in the eDiary will be used. In case the switch of the eDiary from the Treatment Period to the Tapentadol Period was missed, the date of Visit VE will be used for the last IMP intake of the Treatment Period and the first IMP intake of the Tapentadol Period, with time of the day and time missing.

18.1.3 Population heterogeneity during Part 2

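### A missing first-dose time is set to the start of the half-day, so time to first rescue medication is biased one way, by up to 12 hours for the children affected

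*SAP*

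**What the plan says.** SAP section 13.3.2 plans the analysis for Part 1: "The time from first IMP to first rescue medication intake will be summarized using time-to-event methods". Section 18.1.10 gives the derivation. "Time to first rescue medication intake will be calculated in hours as" the date and time of the first rescue intake minus the date and time of the first dose of trial drug.

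The clock time of the first dose comes from the electronic diary. SAP section 18.1.2.11 takes the date and the half-day (morning or evening) from the case report form, and then: "The time will be set to the time of the corresponding eDiary entry at that date and time of the day if available". Without such an entry the clock time is missing.

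For that case section 18.1.10 fixes a value by half-day: "0:00 will be used if the first IMP intake was in the morning and 12:00 will be used" for an evening first dose. Section 7.2.1, the rationale for SAP Amendment 02, states the same rule ("it will be imputed (by 0:00 in case of morning intake or 12:00 in case of evening intake"), so it is intended and not a misprint. Neither section gives a reason for these two values.

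On when the dose is taken, Protocol section 11.1.1.2 places allocation, dispensing of trial drug and rescue medication, and the first intake at Visit V2: "The first dose of IMP will be taken during this visit, within 24 hours after randomization".

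**The concern.** A neutral imputation would sometimes be too early and sometimes too late. This one uses the earliest possible moment, so every error has the same sign: the clock starts too soon and the child appears to go longer without rescue. That is the flattering direction for an analgesic. Elsewhere the SAP defends its conventions as conservative (baseline pain in section 7.2.2, adverse event dates in section 18.1.11.1); here it offers no such argument.

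Because the result is expressed in hours, an error of several hours can be visible in a median. At stake is the accuracy of one descriptive time-to-event summary. The primary endpoint does not use this variable.

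**Working it through.** The documents state no figure to reproduce here, so the check is of direction and size.

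**Direction and bounds.** Take morning as 0:00 to before 12:00 and evening as 12:00 to before 24:00. The SAP does not define them, but its two values imply this. Let *t* be the true clock time of the first dose.

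- Error in time to first rescue = *t* − imputed time.
- Morning: *t* − 0, between 0 and <12 h.
- Evening: *t* − 12, between 0 and <12 h.

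The error is never negative. Censored times of affected children are lengthened in the same way.

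**Size under assumed dosing hours** (none are in the documents):

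| Assumed dose time | Recorded as | Error |
|---|---|---|
| 06:00-10:00 | morning | 6 to 10 h |
| 18:00-22:00 | evening | 18 − 12 = 6 to 22 − 12 = 10 h |
| 08:00-12:00 (site visit) | morning | 8 to 12 h |
| 12:00-18:00 (site visit) | evening | 0 to 6 h |

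**Morning dose on the allocation day.** Allocation on that date happens after its 0:00, and the dose follows allocation and dispensing. The imputed dose therefore precedes the visit at which the drug was handed over. If allocation was the day before, which the 24-hour allowance permits, this particular contradiction does not arise.

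**Effect on a group median (illustration only).** Assume exponential times with true median 12 h, and a share *p* of children with the time missing and a shift of *s* hours. The observed median *m* solves (1 − *p*)·2^(−*m*/12) + *p*·2^(−(*m* − *s*)/12) = 0.5, so *m* = 12 + 12·log2[(1 − *p*) + *p*·2^(*s*/12)].

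- *s* = 8 gives 2^(8/12) = 1.587.
- *p* = 0.10: 12 + 12·log2(1.0587) = 13.0 h.
- *p* = 0.20: 12 + 12·log2(1.1175) = 13.9 h.
- *p* = 0.30: 12 + 12·log2(1.1762) = 14.8 h.
- With *s* from 6 to 10 h: 12.7 to 13.3 h at 10%, and 13.4 to 14.5 h at 20%.

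Simulation gave the same values at 10% and 20%. Of the planned 69 children, 10% is about 7 and 20% about 14. The median, the exponential shape, the shift and the missing share are all assumptions.

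**A neighbouring rule.** SAP section 18.1.11.7 sets a missing first-dose time to 00:00 for time to adverse event onset, whatever the half-day. An evening starter without a recorded time would have two different first-dose times in the same report.

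**The case against.** The strongest defence is that the consequence is small and the present rule has one real merit. Time to first rescue is not a protocol endpoint: Protocol section 8.1.3 names the number of rescue doses, and section 14.2.6.3 focuses on the mean number of daily doses and the mean total daily dose. The SAP adds this summary without a test or decision rule. The first dose is given at Visit V2 with an instruction to record it in the diary, so few times may be missing, and SAP section 18.1.2.8 requires imputed values to be marked in the listings. Because the earliest moment is used, no rescue intake after the true dose can receive a negative time or be dropped. All of this stands. It limits the weight of the point and shapes the fix, but it does not remove the one-way error.

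A reader might infer three stronger things that the documents do not support.

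- *That the error is 6 to 10 h, always before the dose could have been taken.* No clock hours are given. A first dose soon after noon, recorded as evening, would make 12:00 nearly right. For tapentadol out-patients the Visit V2 blood sample is due 1 to 6 h after the dose (Protocol section 1.2.1), so a dose at 18:00-22:00 would put sampling between 19:00 and 04:00. That makes the evening assumption weak.
- *That the comparison of arms is distorted.* The rule is the same in both arms. It favours one only if missing times or dosing hours differ between them, and nothing in the documents shows this.
- *That rescue taken before the first dose will be counted as an event after it.* For an evening starter this is possible, since section 18.1.10 does not address it, but nothing shows that it occurs or how often.

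**Conclusion.** The point holds as a minor one. For a child with a missing first-dose time, the SAP rule makes time to first rescue too long by 0 to <12 h and never too short. For a morning dose on the allocation day the imputed value is wrong on the protocol's own sequence of events. The 0 to <12 h range rests only on reading the two half-days as split at noon; 6 to 10 h needs the assumed dosing hours, and the shifted medians need further assumptions. The number of children affected is not known. The effect is confined to a descriptive summary.

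**What to change.** In SAP section 18.1.10, and correspondingly in section 7.2.1:

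- Impute a missing first-dose time with the median recorded clock time of first morning intakes, or of first evening intakes, pooled over both arms and applied identically in both. If, for example, that median were 08:00 and true doses lay at 06:00-10:00, the error would run from 6 − 8 = −2 h to 10 − 8 = +2 h.
- Use the randomisation time as a lower bound only if a clock time is recorded. SAP section 18.1.2.10 mentions only an allocation date.
- Do not use the pharmacokinetic sample time as a bound. It exists only in the tapentadol arm, with different windows for out-patients and hospitalized children, so the imputation would differ by arm.
- If a rescue intake on the first-dose day falls before the imputed time, do not discard it. Set the imputed first-dose time no later than that intake and flag the record. Discarding it could lose a genuine first event and extend the time to the next rescue or to censoring, an error that could exceed the present one.
- Report the 0:00/12:00 rule as a sensitivity analysis, with the number of imputed times per arm.

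The cost is a change of wording and a little extra programming. Individual imputed times may then err in either direction, in exchange for removing most of the one-way bias.

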18.1.11 Adverse events

The result of all imputation strategies (e.g., incomplete start dates of AE), combination of observations (combination of consecutive AEs) and new derived information (e.g., definition of concomitant medication categories) must be stored in the analysis data set ADAE.

18.1.11.1 Handling of missing date information

The term missing date refers to a completely missing date, or to an incomplete date where parts are not available.

Missing start and end date will be imputed conservatively, i.e., missing values will be imputed in such a way that the duration of the AE is considered with the longest possible duration and such that, whenever the AE may potentially start after first IMP administration, the AE will be handled as a TEAE.

I1-I4: imputation steps,
C1-C4: checkpoints

Figure 2: Graphical overview about the imputation strategy

Further explanations on the flow chart: The different steps of the displayed imputation strategy must be completed from the first to the last step. All procedures in each step must be completed in the order given.

- Imputation:

- I1: impute with date of first IMP.
- I2:
Impute with first calendar day and/or first calendar month.
Imputation will be done based on the available partial information starting with month and then day. The respective first month and day will be chosen for imputation:

Missing date	Imputed date
2014-Mar	2014-Mar-01
2014	2014-Jan-01

- I3: Impute with date of informed consent signed
- I4:
Impute with last calendar day and /or calendar last month
Imputation will be done based on the available partial information starting with month and then day. The respective last month and day will be chosen for imputation:

Missing date	Imputed data
2014-Mar	2014-Mar-31
2014	2014-Dec-31

For February leap years must to be taken into account when calculating the last day in February.

- Checkpoints
 - C1: The decision must to be taken based on the available information (date) before imputation.
 - C2: AE stop date before first IMP
 - 1) The decision must to be taken based on the available information (date) before imputation.
 - 2) If the end date is completely missing (with or without the information that the AE was ongoing) this will be considered as after first IMP.
 - 3) If no IMP was given this will be treated as AE stop date before first IMP.
 - C3: The decision must to be taken based on the available information (date) before imputation.
 - C4: The decision must to be taken based on the available information (date) before imputation.

A replacement of missing year for AE start information is not foreseen. If needed this will be considered on a case-by-case decision which must be documented together with the documentation of ADaM data sets.

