11.1.4 Visit VE (Day 15 ± 1, End of Treatment Visit)

This visit is planned for Day 15 ± 1, but must also be performed within 3 days after last intake of IMP if a subject discontinues IMP during the Treatment Period.

The following procedures will be performed:

- Record age of subject.
- Record concomitant medication intake/therapies.
- Perform a physical examination, document that it was performed, and record changes to previous assessment.
- Record height.
- Record body weight.
- Record vital signs (respiratory rate, systolic and diastolic blood pressure, and pulse rate).
- Record a 12-lead ECG.
- Record “pain right now” in the CRF (VAS and FPS-R) - only for subjects going into the Tapentadol Period.
- Complete the following questionnaires:
 - Modified CAS.
 - Acceptability and palatability of IMP.
 - Dispense SOWS questionnaire for completion at home if this is the visit of the last intake of IMP (only for subjects going in to the Observation Period). To be completed once daily until the seventh day after the last intake of IMP. To be collected at Visit F7D.
- Check diary compliance.
- Collect the diary for subjects not entering the Tapentadol Period (Part 2).
- Collect returned IMP and rescue medication.
- Perform drug accountability:
 - Confirm and document compliance with IMP intake.

Confidential

Protocol KF5503-66
including Amendment 05

Page 63 of 137
DMS version 9.0
27 Jul 2017

- Confirm whether returned amount of rescue medication matches expected amount to be returned.
- Verify discrepancies with subject, or parent(s), legal guardian(s), or caregiver.
- Take blood sample for serum pharmacokinetics (at any time during the visit, but after measuring the pain scores) from subjects on tapentadol PR.
- Take blood for central laboratory (hematology, clinical chemistry).
- Collect urine/perform dip stick urinalysis.
- Perform a urine pregnancy test in female subjects who are post-menarchal or older than 12 years at the time of the scheduled visit.
- Assess and record adverse events. Document changes (e.g., in the intensity) of each ongoing adverse event.
- Check discontinuation criteria for IMP intake.
- Check subject eligibility and assign eligible subjects to the Tapentadol Period or Observation Periods.

For subjects entering the Tapentadol Period:

- Instruct the subject, parent(s), legal guardian(s) or caregiver about the Tapentadol Period, including:
 - Discuss titration/dose adjustment if subject transfers from morphine PR.
 - Dispense IMP.

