11.1.2 Part 2 – Tapentadol Period

Subjects completing the Treatment Period (Part 1) with tapentadol PR or morphine PR and who have need for continued opioid treatment can enter the Tapentadol Period. Assignment to the Tapentadol Period needs to be documented in the CRF and the interactive response technology system. Subjects will be followed until Visit F12M. Subjects in the Tapentadol Period of Part 2 may stop treatment early (before Visit F12M) and switch to Observation period for the remainder of Part 2.

11.1.2.1 Visit M1 (Day 7 ± 2) and Visit M2 (Day 14 ± 2)

As withdrawal symptoms may occur in subjects transferring from morphine PR to tapentadol PR, because they start tapentadol PR at 70% of the equivalent morphine dose, these subjects will have 2 additional visits at the beginning of the Part 2 Tapentadol Period (Visit M1 and Visit M2).

Confidential

Protocol KF5503-66
including Amendment 05

Page 64 of 137
DMS version 9.0
27 Jul 2017

Visit M1 and Visit M2 in the Tapentadol Period are only for subjects who had been previously allocated to morphine PR in the Treatment Period.

The following procedures will be performed:

- Record concomitant medication intake/therapies.
- Record vital signs (respiratory rate, systolic and diastolic blood pressure, and pulse rate).
- Record “pain right now” in the CRF (VAS and FPS-R).
- Train/instruct subject(s), parent(s) or legal guardian(s) how to use the diary.
 - Give instructions to record intake of IMP in the diary, including time of administration.
- Check diary compliance.
- Collect returned IMP.
- Perform drug accountability:
 - Confirm and document compliance with IMP intake.
 - Verify discrepancies with subject, or parent(s), legal guardian(s), or caregiver.
- Dispense IMP.
- Discuss titration/dose adjustment.
- Train/instruct subject, parent(s), legal guardian(s), or caregiver on the use of IMP (handling and intake). Exchange instruction sheet if necessary (e.g., due to weight change).
- Assess and record adverse events.
- Check discontinuation criteria.

11.1.2.2 Visit TP1 to TP12 (every 28 days after Visit VE, range: ±5 days)

Visits TP1 to TP12 are performed at ~28 day intervals in all subjects in the Tapentadol Period. The following procedures will be performed:

- Record concomitant medication intake/therapies.
- Record body weight.
- Record height (only at Visit TP3, Visit TP6, Visit TP9, and Visit TP12).

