8.2.2 Further definitions

Term	Part/Period	Definition
Pre-treatment-period	-	Before first IMP administration (excluded)
Therapeutic reach	-	
The therapeutic reach is the time after the last IMP intake that a subject is still considered to be potentially affected by a study drug.
 
For tapentadol PR and morphine PR, the therapeutic reach is defined as 72 hours after (last) IMP intake.

On-treatment-period	Part 1	
 • Subjects continuing in the Tapentadol Period after the Treatment Period: 
 a. Start: First IMP administration of Part 1 (included) b. End: 
 i. If the last administration of IMP during Part 1 is more than 3 days before Visit VE: Last administration of IMP during Part 1 + 72 hours (included, therapeutic reach) ii. If the last administration of IMP during Part 1 is less than 3 days before Visit VE: Visit VE (included) c. Start: First IMP administration (included) d. End: Last administration of IMP during Part 1 + 72 hours (included)
	Part 2	
Tapentadol Period only:
 
 a. Start: Visit VE (excluded in case VE is included in the on-treatment period of Part 1; included in case VE is not included in the on-treatment period of Part 1) b. End: Last administration of IMP during the Tapentadol Period + 72 hours (included)
Post-treatment-period	-	After last IMP administration drug intake + 72 hours (excluded)
Enrolled subjects	-	Informed consent form signed. If required by local law an assent form signed.
Treated subjects	-	Subjects with at least 1 administration of IMP.
Treatment completers	Part 1	
Subjects who have completed the 14-day Treatment Period.
 
Completion of the 14-day Treatment Period means that a subject performs the End of Treatment Visit (Visit VE) in the allowed window of 15 ± 1 days, i.e., at or later than Day 14, and has the last IMP intake of part 1 no earlier than Day 13 in the evening.

	Part 2	
Subjects who have completed the 12-month Tapentadol Period.
 
Completion of the 12-month Tapentadol Period means that a subject performs the 12-month follow-up visit (F12M) in the window of 365 ± 14 days, i.e., at or later than 351 days after Visit VE, as part of the Tapentadol Period.

Trial completers	Part 1	Subjects who have completed the 14-day Treatment Period and who performed Visit F7D or entered the Tapentadol Period of Part 2.

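### The AE start-date imputation protects only the first-IMP boundary, so a month-only event that begins after Visit VE in VE's calendar month is dated back into Part 1

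*SAP*

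**What the plan says.** SAP 18.1.11.1 imputes incomplete AE dates so that the event has its longest possible duration, and so that "whenever the AE may potentially start after first IMP administration, the AE will be handled as a TEAE". The steps it names are "I1: impute with date of first IMP", then I2, "Impute with first calendar day and/or first calendar month", then "I3: Impute with date of informed consent signed", and finally I4, "Impute with last calendar day and /or calendar last month". I4 gives a late date, so under the longest-duration principle it can serve only end dates.

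SAP 15.1.2 and 18.1.11.3 decide which period a TEAE belongs to after this replacement. For children who continue into the Tapentadol Period, SAP 8.2.2 sets the end of the Part 1 on-treatment period: "If the last administration of IMP during Part 1 is less than 3 days before Visit VE: Visit VE (included"). Part 1 is presented by arm (SAP 8.1), and the Safety Set is analysed by treatment actually received (SAP 9.3). SAP 18.1.2.11 defines the first IMP intake of the Tapentadol Period, but 18.1.11.1 does not use it.

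**The concern.** The rule is conservative for one question only: TEAE or not. This trial has a second boundary. At VE the continuing morphine-arm children change drug, and all continuing children change analysis period. The protocol regards the weeks after that change as sensitive: "As withdrawal symptoms may occur in subjects transferring from morphine PR to tapentadol PR", which is why Visits M1 (Day 7) and M2 (Day 14) were added. Protocol 14.2.7.1 likewise counts a worsening in the Tapentadol Period of a former morphine child as a new TEAE.

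Tolerability by arm and period is a main secondary endpoint (SAP 15.1). If partial dates around VE always resolve backwards, onsets under Part 2 tapentadol are lost as new events from the Tapentadol Period tables by preferred term and from the exposure-adjusted rates (SAP 15.1.2.3). For former morphine children they enter the morphine column of Part 1.

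**Working it through.** **Inputs from the documents.** Steps I1 to I3 (SAP 18.1.11.1); period assigned after imputation (SAP 18.1.11.3); Part 1 on-treatment ends at VE, inclusive, for continuing children whose last Part 1 intake was less than 3 days earlier (SAP 8.2.2); 69 children at 2:1 (SAP 5.2), that is 69/3 = 23 on morphine and 46 on tapentadol.

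**Assumptions.** VE dates are spread evenly over the year; the month is known and the day is missing; first IMP in I1 means first IMP of the trial.

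**Step 1: the plan's own examples.** Under I2, 2014-Mar becomes 2014-Mar-01 and 2014 becomes 2014-Jan-01. Both reproduce.

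**Step 2: which events move.** Take an onset after VE in the same calendar month as VE. I1 gives first IMP and I2 gives the first of that month. Both are on or before VE, so the event falls in Part 1. An onset in a later month goes under I2 to the first of that later month, which is after VE, and stays in the Tapentadol Period.

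*Example:* first IMP 2 March 2016, VE 16 March. A true onset on 20 March recorded as March 2016 becomes 2 March, so Part 1. A true onset on 10 April recorded as April 2016 becomes 1 April, so Tapentadol Period, which is correct.

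**Step 3: how often.** An onset s days after VE (s up to 28) lies in VE's month with probability 1 − 12s/365. Averaged over s = 1 to N:

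share moved = 1 − 12(N + 1)/(2 × 365)

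- N = 14: 1 − 180/730 = 75.3%
- N = 28: 1 − 348/730 = 52.3%

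Enumerating every first-IMP date from 2015 to 2017 gives nearly the same:

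| Onset after VE | Moved into Part 1 |
|---|---|
| Days 1–7 | 86.9% |
| Days 1–14 | 75.4% |
| Days 1–21 | 63.9% |
| Days 1–28 | 52.4% |

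The results are identical for VE on Day 14, 15 or 16. The longest lag that still moves is 30 days. If only the year is known, 96.0% of onsets in days 1–28 move.

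**Step 4: the reverse error.** No start-date step moves a Part 1 onset past VE: 0 of 16,440 enumerated Part 1 onsets did so.

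**Step 5: scale.** One moved child is 1/23 = 4.3 percentage points in a morphine row, if that child has no other Part 1 event in the row. The documents give neither AE counts nor a rate of incomplete dates. As an illustration only: if all 23 morphine children switch, each has 2 AEs in 28 days, and 1% to 5% of start dates lack the day, then 23 × 2 × (0.01 to 0.05) × 0.52 = 0.2 to 1.2 events.

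**The case against.** A reader might infer that the rule tilts the randomised comparison in tapentadol's favour. The documents do not support that. Tapentadol-arm children who continue are back-dated by the same rule, and allocation gives twice as many of them (46 against 23). Their events stay under tapentadol and raise that Part 1 column too. The net effect depends on how post-VE event rates differ between switchers and continuers, which nothing in the documents gives.

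A reader might also infer that the events disappear from the Tapentadol Period. They do not: SAP 15.1.2.1 counts Part 1 TEAEs that are ongoing in the Tapentadol Period, in the overviews of both periods. Original and imputed dates are both displayed (SAP 18.1.2.7), and imputed values are marked in the listings (SAP 18.1.2.8). Safety is descriptive, without tests between arms (SAP 15).

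Data quality should also be good here. AEs are assessed at VE, M1 and M2, and the eCRF raises automatic queries for missing data (Protocol 13.3). This limits the number of events, not the mechanism.

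Onsets within 72 hours of the last morphine intake lie within the SAP's own therapeutic reach. That blurs drug attribution in the first days. Even so, with a complete date after VE, SAP 8.2.2 would put such an event in the Tapentadol Period, so the imputation still overrides the plan's own period rule.

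Finally, the flow chart (Figure 2) is not available here, and the branch conditions at C1, C3 and C4 are not in the text. The direction survives this: no listed start value lies after VE for an onset in VE's month. The shares do rest on I2 being used for later months; if I1 were used there, more events would move, not fewer. The consent-date step gives a date before treatment and does not drive the effect.

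**Conclusion.** The point holds as a gap in the imputation rule. On the listed values, a month-only onset after VE in VE's calendar month is placed in Part 1: about 75% of such events in the first 14 days and 52% in the first 28, under evenly spread dates. The error in period runs one way. It under-counts new TEAEs in the Tapentadol Period tables and, for former morphine children only, shows an onset on tapentadol under morphine. The percentages apply only to events with an incomplete start date, whose number the documents do not give. The matter is minor, and worth correcting because a stated rule gives a wrong period, and for switchers a wrong drug, on a main secondary endpoint.

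**What to change.** Add one condition to SAP 18.1.11.1. If a partial start date is compatible with both Part 1 and the Tapentadol Period, and the event was first recorded after Visit VE, impute the date of the first Tapentadol Period intake and assign the event to that period. Keep I1 and I2 for events already on record at VE and for the TEAE versus non-TEAE decision. Where this cannot be decided, flag the event and tabulate it both ways, rather than sending it to either period by default.

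Whether an event was on record at VE can usually be established. The VE procedures in the protocol include "Document changes (e.g., in the intensity) of each ongoing adverse event", and eCRF entries carry a date and time stamp (Protocol 13.1). The AE fields listed in Protocol 12.6.1 include no visit of first report, so the stamp may have to serve. Entry can lag the visit, so a stamp only shortly after VE should count as undecided.

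The cost is a little programming, and a late-reported Part 1 event may occasionally be placed in the Tapentadol Period. The change should be made before the data snapshot for the final analysis of Part 1.
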